7.6 Outcome measures

The primary outcome measure will be the total number of mature (MII) oocytes adjusted by antral follicle count (AFC) available for cryopreservation.

Secondary outcome measures will include the following:

- Total number of oocytes retrieved per cycle
- Ratio of mature (MII) to immature oocytes
- Total number of mature oocytes (MII) retrieved per IVF/ICSI cycle
- Oocyte yield (defined as the number of metaphase II (MII) oocytes retrieved divided by the number of follicles ≥15 mm on ultrasound on the day of trigger)
- "Follicular Output Rate" (FORT) (defined as ratio of pre-ovulatory follicles (16-22mm) on day of trigger × 100/AFC (3-8mm) [22]
- Incidence of moderate to critical OHSS based on the classification criteria by Golan et al [26].
- If the embryos are frozen:
 - o Fertilization rate, which will include two outcomes each defined as follows:
 - Definition 1: number of 2PN zygotes divided by the number of mature oocyte(s) fertilized per IVF/ICSI cycle.
 - Definition 2: number of 2PN zygotes divided by the number of oocytes incubated with at least 10,000 sperm per IVF cycle.
 - Total number of good quality day 5 embryos available for cryopreservation determined by an embryologist using the classification system by Gardner and Schoolcraft, 1999 [25].
- Dose-adjusted evaluation of the safety and tolerability of follitropin alfa + lutropin alfa compared to follitropin alfa as measured by incidence of:
 - o Treatment-emergent adverse events (TEAEs)
 - Treatment-related adverse events (AEs)
 - o Incidence of thromboembolic events

8. Study methods

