A cohort study by Johnson et al. [16] examined the ovarian stimulation response in oncology fertility preservation patients under various IVF stimulation protocols which included the use of rLH in some patients. The study showed no overall difference in baseline measures of ovarian reserve, total dose of gonadotropin used, or mean number of oocytes retrieved in the group of 50 chemotherapy-naïve cancer patients compared to 50 matched healthy controls. Unfortunately, the number of patients receiving rLH and the total dose received by these patients was not specified. Other studies in the literature examining rLH included case reports and case series, with sample sizes insufficient to generate conclusions regarding rLH efficacy in cancer patients [17-19]. A systematic review concluded that research on ovarian stimulation protocols and outcomes in the onco-fertility literature was inconsistent and of low quality [20], calling for higher quality studies to provide clarity on this topic.

Therefore, we intend to conduct an exploratory randomized controlled trial (RCT) comparing FSH and LH versus FSH alone using a GnRH antagonist protocol in non-hormone sensitive cancer patients undergoing fertility preservation. These patients include those diagnosed with malignancy other than breast, uterine and ovarian cancer.

3. Study Question

In non-hormone sensitive cancer patients undergoing IVF fertility preservation, does the use of FSH and LH for ovarian stimulation lead to a greater proportion of mature oocytes available for cryopreservation relative to AFC compared to FSH alone?

We theorize that supplementation with FSH + rLH will increase the yield of mature MII oocytes among patients with non-hormone sensitive cancer undergoing fertility preservation compared to those with FSH alone. In addition, we anticipate the following trends among patients in the FSH + rLH group compared to those supplemented with FSH alone:

- Higher number of total oocytes retrieved per cycle
- Higher "Follicular Output Rate" (FORT), defined as ratio of pre-ovulatory follicles (16-22mm) on day of trigger divided by AFC [22]
- Higher number of cryopreserved embryos (if patient chooses to freeze embryos rather than oocytes)
- No significant difference in incidence of moderate-severe OHSS

5. Rationale

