12.1 Sample Size

A sample size calculation was performed according to the primary outcome of the total number of mature oocytes available for cryopreservation [28]. We assume the control group will have a mean of 8 cryopreserved oocytes with a standard deviation of 4 according to data from a previous meta-analysis of randomized trials evaluating FSH and LH versus FSH alone using a GnRH antagonist protocol [29]. We will use an alpha level of 5%, power of 80%, enrolment ratio of 1, and assume a 20% improvement in FSH and LSH versus FSH alone. This calculation will yield a sample size of 126 patients (n=63 per group). Accounting for 10% loss to follow-up, the total sample size will be 140 patients (n=70 per group). Reported p-values will be recorded as two-tailed. The following formula was used for sample size calculation, which was doubled to account for two trial arms and multiplied by 1.1 to account for 10% loss to follow-up:

$$n_1 = \frac{(\sigma_1^2 + \sigma_2^2/K)(Z_{1-\frac{\alpha}{2}} + Z_{1-\beta})^2}{|u_2 - u_1|^2}$$

$$n_1 = \frac{(4^2 + 4^2/1)(1.96 + 0.84)^2}{|10 - 8|^2}$$

$$n = 63 * 2 * 1.1$$

Where n_1 is the sample size for the FSH and LH group; σ_1^2 is the variance for FSH and LH group; σ_2^2 is the variance for the FSH only group; $Z_{1-\frac{\alpha}{2}}$ is the Z-score corresponding to an alpha level of 0.05; $Z_{1-\beta}$ is the Z-score corresponding to a power of 0.80; u_1 is the projected mean number of cryopreserved oocytes in the FSH and LH group; u_2 is the projected mean number of cryopreserved oocytes in the FSH only group; n is the total sample size after accounting for projected loss to follow-up

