12.2 Planned analysis

The analysis will be performed on an intention-to-treat principle. Continuous variables will be examined for normality using a normal probability plot. Normally distributed continuous variables will be compared using Welch's t-test. Continuous variables not normally distributed will be compared using Mann-Whitney U test. Categorical data will be reported as counts with percentage, and compared with chi-square test or Fisher's exact test whenever appropriate. Additional sensitivity analysis will be performed taking into account potential confounding factors (i.e. Age, AMH, AFC). Regression analysis with age and FSH dose as factors will also be performed. Statistical analysis will be performed using R statistical software (R Foundation for Statistical Computing).

13. Trial registration

The clinical trial will be registered and available online at www.clinicaltrials.gov once the protocol is approved by the Mount Sinai Hospital Research Ethics Board.

14. Knowledge translation

The lack of consensus on the safety and efficacy of rLH in addition to FSH for ovarian stimulation calls for high quality randomized trials. Once the trial is completed and results are available, knowledge translation is of critical importance and involves the translation of findings to policy and practice [30]. Several procedures will be implemented to share the results of this trial internationally given the increasing number of young patients diagnosed with cancer. The study results will be firstly presented at international fertility conferences. The results will also be published in a high impact fertility journal, such as *Human Reproduction*. Experts in the field will be contacted to ensure they are aware of trial results.

15. Role of principal investigator

[name] is a reproductive endocrinologist at Mount Sinai Fertility as well as a Professor in the Department of Obstetrics and Gynecology at Mount Sinai Hospital. She will be supervising all aspects of the trial.

16. References

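### The declared primary outcome is the AFC-adjusted number of mature oocytes, but the trial is sized on the unadjusted number, so 80% power is not established for the primary outcome

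*Protocol*

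**What the plan says.** Protocol Section 7.6 defines the primary outcome: "The primary outcome measure will be the total number of mature (MII) oocytes adjusted by antral follicle count (AFC) available for cryopreservation". Its list of secondary outcomes includes "Total number of mature oocytes (MII) retrieved per IVF/ICSI cycle", so the protocol itself treats the adjusted and unadjusted numbers as two outcomes. The study question in Section 3 agrees with the adjusted version. It asks whether adding LH would "lead to a greater proportion of mature oocytes available for cryopreservation relative to AFC compared to FSH alone".

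Section 12.1 goes the other way: "A sample size calculation was performed according to the primary outcome of the total number of mature oocytes available for cryopreservation". Its inputs are on the unadjusted scale: "We assume the control group will have a mean of 8 cryopreserved oocytes with a standard deviation of 4", with 10 versus 8 oocytes in the formula. The design statement in Section 7.1 also refers to the unadjusted number.

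Section 12.2 compares continuous variables with Welch's t-test or the Mann-Whitney test, depending on normality. AFC enters only here: "Additional sensitivity analysis will be performed taking into account potential confounding factors (i.e. Age, AMH, AFC"). The other planned model leaves AFC out: "Regression analysis with age and FSH dose as factors will also be performed".

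**The concern.** Two sections name different primary outcomes, and the sample size supports only one of them. What adjustment by AFC means is not defined, and each reading leaves a gap:

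- **Ratio MII/AFC.** The tests in Section 12.2 can be applied to it, but Section 12.1 sizes another variable.
- **Regression with AFC as a covariate.** The SD of the raw count can carry over, but Section 12.2 gives AFC a role only in a sensitivity analysis.

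The raw count and the ratio can lead to different conclusions in the same data. With an outcome section supporting one and a sample-size section supporting the other, either could be presented as the primary result. The trial is open-label, so that choice could be made after results by arm are known.

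**Working it through.** **Inputs from Section 12.1.** Control mean 8, SD 4 (CV 4/8 = 0.5), difference 10 − 8 = 2 (25% of 8), two-sided 5%, 80% power, 1:1 allocation.

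**1. The plan's own figure.** n per group = (4² + 4²)(1.96 + 0.84)² / 2² = 62.7, so 63. Power at 63 per group is Φ((2/4)·√(63/2) − 1.96) = 80%. The figure reproduces for the raw count.

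**2. Ratio MII/AFC.** The protocol gives no CV for this ratio, so a range is assumed, with a 25% gain and equal SDs. Power = Φ((0.25/CV)·√(63/2) − 1.96). Patients per group for 80% power = 2·(CV/0.25)²·(1.96 + 0.84)².

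| CV of MII/AFC (assumed) | Power at 63 per group | Needed per group for 80% |
|---|---|---|
| 0.4 | 94% | 41 (40.1) |
| 0.5 | 80% | 63 (62.7) |
| 0.6 | 65% | 91 (90.3) |
| 0.7 | 52% | 123 (122.9) |

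**3. When the ratio does no worse than the raw count.** Let c be the CV of AFC and r its correlation with MII. To first order, CV²(MII/AFC) = 0.5² + c² − 2·r·0.5·c = 0.25 + c² − r·c. This is at most 0.25 only if r ≥ c. The centre's regression in Section 8.2 reports an association between AFC and mature oocytes but no strength, so the condition cannot be checked from the protocol.

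**4. AFC as a covariate.** The residual SD is 4·√(1 − r²), so the standardised effect is 0.5/√(1 − r²). By the noncentral t with 63 per arm, power is 81%, 83% and 90% at r = 0.2, 0.3 and 0.5. On this reading the raw-count sizing is slightly conservative.

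**5. Simulation check.** Lognormal MII (mean 8, SD 4), lognormal AFC (mean 15), 2 oocytes added in the treatment arm, 63 per arm, 3,000 to 4,000 trials per setting. The AFC distribution and the correlations are assumptions.

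| Analysis (Welch or regression) | AFC CV 0.4; r = 0.2, 0.3, 0.5 | AFC CV 0.53; r = 0.2, 0.3, 0.5 |
|---|---|---|
| Raw count, Welch | 79–80% | 79–80% |
| Ratio, Welch | 67%, 75%, 91% | 55%, 64%, 82% |

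Regression on arm and AFC gave 81–89% over the same settings. The raw and ratio Welch tests disagreed on significance in roughly 20% to 35% of simulated trials.

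**6. A separate matter that affects the figures.** The text of Section 12.1 says "assume a 20% improvement in FSH and LSH versus FSH alone", that is 0.20 × 8 = 1.6 oocytes, while its formula uses 2. At 1.6, raw-count power is about 61%, and covariate-adjusted power about 62%, 65% and 73% at r = 0.2, 0.3 and 0.5. That drop comes from the 20%/25% conflict, not from the outcome mismatch.

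**The case against.** The best counter-argument accepts the clash between Sections 7.6 and 12.1 and disputes what follows from it.

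- **The ratio figures rest on assumptions, and Welch is not the test the plan would use for skewed data.** Section 12.2 would send a skewed ratio to the Mann-Whitney test. In the same simulation this raises ratio power to about 68–95%. That is a fair correction to the Welch figures. Raw-count power also rises under Mann-Whitney, to about 92%, so power still depends on which outcome is tested. At correlations above 0.5 the ratio would do well even under Welch. All this supports calling the power unknown rather than low.
- **The form of adjustment can be left to an SAP.** This is true of model detail. It does not cover two protocol sections naming different primary outcomes: an SAP that follows one still contradicts the other.
- **Section 3 points to a ratio, so there is little ambiguity.** The ratio is the more natural reading of the study question. If it is intended, Section 12.1 has been calculated for the wrong variable, which is the point at issue.
- **The trial calls itself exploratory.** It still claims 80% power, and Section 6 expects its result to guide counselling.

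**Conclusion.** The concern holds. Sections 7.6 and 12.1 name different primary outcomes, and 80% power at 63 per group is supported only for the raw count with a difference of 2 oocytes and SD 4. For the ratio, power for a 25% gain runs from about 94% down to 52% over assumed CVs of 0.4 to 0.7. For a covariate-adjusted count it is about 81% to 90% over assumed correlations of 0.2 to 0.5.

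The contradiction itself needs no assumption. The size of its effect on power does, because the protocol gives no CV for the ratio, no AFC distribution and no correlation. The conclusion is that power for the declared primary outcome is not established; it may be lower or higher than 80%. This must be fixed, since it determines which result decides the trial.

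**What to change.** Use one definition of the primary outcome in Sections 3, 7.1, 7.6, 12.1 and 12.2.

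**Simplest option.** Make the primary outcome the number of MII oocytes per randomised patient, compared between arms in a regression with AFC as a covariate. State this in Section 12.2 as the primary analysis and make MII/AFC secondary. The raw-count SD then carries over and is conservative for a given difference. The power must be restated once the 20% versus 25% conflict in Section 12.1 is settled. The cost is that the ratio loses primary status and Section 3 is reworded.

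**Alternative, if the sponsor wants the ratio as primary.** Define it as MII/AFC in all five sections, give its control mean, SD and target effect in Section 12.1, and restate the power or sample size. The centre's retrospective data could supply these inputs. This stays closest to Sections 3 and 7.6. The cost depends on the ratio's CV: for a 25% gain, 41 per group would suffice at 0.4, while 91 to 123 would be needed at 0.6 to 0.7, before drop-out.

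Either way this is a protocol amendment without new data collection, since AFC is already recorded (Section 7.5). It should be made before any results by arm are examined.

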A daily, subcutaneous injection of a GnRH antagonist (Cetrotide or Ganirelix 0.25 mg) will be administered by the patient subcutaneously to prevent an endogenous surge in LH. Monitoring of the ovarian response will continue until there are 3 or more follicles visualized by transvaginal ultrasound with a mean diameter of ≥17 mm. Ovulation will be subsequently triggered with a subcutaneous injection of HCG or GnRH agonist depending on the managing IVF physician. If a GnRH agonist trigger is chosen, twelve hours after their trigger medication, patients will return to the clinic for blood work including LH and progesterone as per standard procedure. This is a routine confirmatory blood test to confirm that an endogenous LH surge has occurred. In approximately less than 5% of cases, the GnRH agonist trigger fails to elicit an optimal surge, which may require a "rescue" low-dose hCG trigger to be administered 24 hours following the initial trigger. The decision to administer a "rescue" trigger will be at the discretion of the managing IVF physician. Transvaginal, ultrasound-guided oocyte retrieval will be performed approximately 36 hours following the administration of the initial trigger.

Once the oocytes are retrieved, if the patient desires to cryopreserve oocytes, mature oocytes will be cryopreserved by vitrification process. If embryo cryopreservation is planned, the retrieved oocytes will be fertilized in the lab using traditional IVF or ICSI. Embryos will be grown to day 5 and all "good quality" blastocysts will be cryopreserved using vitrification. At our clinic, day 5/6 embryos are considered "good quality" for cryopreservation if they are at least a grade 2BB (or above) on day 5 and/or a 3CC (or above) on day 6, according to the classification system by Gardner and Schoolcraft, 1999 [25].

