7.5 Data collection

The following demographic information will be collected from included patients:

Demographics

- Age
- Gravida/para status
- BMI
- Type of malignancy
- Stage of malignancy (if known)
- Prior history of fertility treatment and the specific type
- Baseline FSH, LH, progesterone, estradiol levels
- Ovarian reserve: AMH and AFC (3-8mm) based on the FORT criteria [22].
- Any history of infertility, categorized as:
 - Anovulation including PCOS
 - o Tubal
 - Male Factor Infertility
 - Endometriosis
 - o Unexplained
 - o Other
 - o None
- Total motile sperm count (if freezing embryos)

Characteristics of treatment cycle

- Type of cycle start (follicular vs. luteal phase)
- Total days of gonadotropin stimulation
- Total dose of FSH (IU)
- Total dose of LH (IU)
- Total number of follicles measuring ≥11 mm on the day of trigger
- Total number of follicles measuring 16-22 mm on the day of trigger, according to FORT criteria [22]
- Type of trigger (hCG vs. GnRH-agonist)
- Need for rescue hCG trigger (ie. failed GnRH agonist trigger)
- Bloodwork on day of trigger ± day after trigger:
 - o E2
 - o LH
 - o Progesterone
- Method of fertilization (standard insemination or ICSI or IVF/ICSI split) if freezing embryos
- Use of a dopamine receptor agonist (Cabergoline) to prevent OHSS

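### Two secondary outcomes are poorly defined: the mature-to-immature ratio has no value when every oocyte is mature, and the embryo count stops at day 5 although day-6 embryos are also graded for freezing

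*Protocol*

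**What the plan says.** **Maturity.** Protocol Section 7.6 gives the outcome as "Ratio of mature (MII) to immature oocytes" and nothing more. Oocyte yield and FORT, in the same list, each have numerator and denominator spelled out. Total oocytes retrieved and total MII oocytes are separate secondary outcomes in that list.

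**Embryos.** For patients who freeze embryos, Section 7.6 counts "Total number of good quality day 5 embryos available for cryopreservation". Section 7.1 says "Embryos will be grown to day 5", but its definition of good quality covers day 5 and day 6 and includes a separate threshold of "3CC (or above) on day 6". The expected trends listed after the study question in Section 3 include "Higher number of cryopreserved embryos (if patient chooses to freeze embryos rather than oocytes"), with no restriction by day.

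**Follicles.** Oocyte yield in Section 7.6 is the number of MII "oocytes retrieved divided by the number of follicles ≥15 mm on ultrasound on the day of trigger". The cycle data in Section 7.5 include "Total number of follicles measuring ≥11 mm on the day of trigger" and a 16-22 mm count for FORT, but no count from 15 mm upwards.

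**Analysis.** Section 12.2 applies Welch's t-test to continuous variables that look normal and the Mann-Whitney test to the rest, on the intention-to-treat principle, and adds regression analyses.

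**The concern.** A ratio of mature to immature oocytes fails for the patients with the best maturation. With no immature oocyte it has no finite value, so it cannot enter a mean, a Welch's t-test or a linear regression. The protocol does not say how such patients are handled. If they were left out, the loss would not be random: an arm with better maturation would lose more of its best patients, and a true benefit of rLH would be understated. Maturation is central to the trial's reasoning, since Section 5 cites a greater share of immature oocytes in cancer patients.

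The embryo outcome can be computed as written, but it is narrower than the hypothesis it is meant to address. Read literally, it leaves out an embryo that reaches the day-6 freezing grade. Section 7.1 is also at odds with itself on whether culture ends at day 5. Day-6 embryos could therefore be counted for some patients and not for others.

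The follicle item is a mismatch between two lists. It does not make oocyte yield impossible to compute.

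**Working it through.** **1. How the ratio behaves.** Take 10 oocytes retrieved.

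| Mature | Immature | Mature / immature | Mature / total |
|---|---|---|---|
| 8 | 2 | 4 | 0.8 |
| 9 | 1 | 9 | 0.9 |
| 10 | 0 | no value | 1.0 |

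Each row differs by one oocyte. The proportion moves in equal steps. The ratio more than doubles and then ceases to exist.

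**2. How often it is undefined.**

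Inputs from the protocol: Section 12.1 states "We assume the control group will have a mean of 8 cryopreserved oocytes with a standard deviation of 4", read here as MII oocytes per patient, and 63 evaluable patients per arm. The 63 reproduces from the plan's formula: (16 + 16) × (1.96 + 0.84)² / 2² = 62.7.

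Assumption: the share of retrieved oocytes that are mature, *m*, is not given, so 0.70 to 0.90 is used. Oocytes are treated as independent.

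*Fixed number retrieved, 10:* P(no immature) = *m*¹⁰ = 0.028, 0.107 and 0.349 for *m* = 0.7, 0.8 and 0.9.

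*Varying number retrieved, negative binomial.* A mature count with mean 8 and variance 16 has dispersion parameter 8² / (16 − 8) = 8. The number retrieved then has the same parameter and mean 8/*m*, and the immature count has mean 8(1 − *m*)/*m*. So P(no immature) = [1 + (1 − *m*)/*m*]⁻⁸ = *m*⁸. Patients with no oocyte at all, P(none) = (1 + 1/*m*)⁻⁸, are then removed.

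| *m* | Retrieved, mean (SD) | *m*⁸ | P(none) | Undefined, given at least one oocyte | Of 63 per arm |
|---|---|---|---|---|---|
| 0.70 | 11.4 (5.3) | 0.058 | 0.001 | 0.057 | 3.6 |
| 0.80 | 10.0 (4.7) | 0.168 | 0.002 | 0.167 | 10.5 |
| 0.90 | 8.9 (4.3) | 0.430 | 0.003 | 0.429 | 27.0 |

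A variant that instead gives the number retrieved a coefficient of variation of 0.5 yields 6.6%, 17.4% and 43.2%, counting the 0.2-0.3% with no oocyte.

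**3. What exclusion would do.** This applies only if patients without a ratio are dropped. Let *u* be the undefined share in an arm. Those patients all have a mature proportion of 1, so the mean proportion among the rest is (*m* − *u*)/(1 − *u*). With a mean of 10 retrieved and SD 4.8 in both arms:

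| *m* | *u* | Mean proportion among those left |
|---|---|---|
| 0.70 | 0.078 | 0.675 |
| 0.80 | 0.168 | 0.760 |
| 0.90 | 0.390 | 0.836 |

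A true gain of 0.10 becomes 0.760 − 0.675 = 0.085 (70% v 80%) or 0.836 − 0.760 = 0.076 (80% v 90%). The better arm loses more patients: 17% against 8%, or 39% against 17%.

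**4. Embryo wording, side by side.** The hypothesis covers all cryopreserved embryos. The freezing rule in Section 7.1 covers day 5 and day 6, each with its own grade. The culture statement in Section 7.1 stops at day 5. The outcome in Section 7.6 covers day 5 only. These four cannot all describe the same set of embryos. The share frozen on day 6 is not given, so no size is put on this.

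**5. Follicle counts.** A count at or above 11 mm also includes follicles from 11 mm to below 15 mm. A 16-22 mm count misses those from 15 mm to below 16 mm and any above 22 mm. Neither count, nor the two together, gives the number at or above 15 mm.

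**The case against.** How to treat a zero denominator is a rule that a statistical analysis plan commonly supplies, and that plan is not at hand. The protocol nowhere says these patients are excluded, and Section 12.2 states intention to treat. A variable that jumps from 4 to 9 to no value is unlikely to look normal, so the Mann-Whitney test would probably be chosen. The ratio equals *p*/(1 − *p*), where *p* is the mature proportion, so with all-mature patients ranked highest that test gives the same result as one on *p*. Both component counts are reported anyway. The shares in the working depend on an assumed maturity rate, and Section 5 suggests that cancer patients may sit towards the lower end, about 4 of 63 per arm. A day 5 count is a legitimate endpoint that fits the statement on culture length, and Section 7.5 is plainly not a full list of what will be recorded.

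Much of this stands. The bias is conditional on exclusion, the rank test can be rescued, and the follicle point alone would not merit comment. What remains is that the protocol itself chose the ratio. A later rule can only patch it, and no rule gives an all-mature patient a natural value for a mean, a t-test or a regression. A better measure is available from counts already planned. The day 5 and day 6 statements disagree within the protocol, and no analysis plan can settle that without departing from one of them.

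**Conclusion.** The concern holds and should be corrected, though it does not threaten the trial's main result. The ratio is undefined for all-mature patients: about 6% to 43% of patients for an assumed maturity of 70% to 90%, with the planning mean and SD read as MII per patient, or 3% to 35% with exactly 10 oocytes retrieved. Exclusion, which the protocol does not prescribe, would shrink an assumed 10-point gain to about 8.5 or 7.6 points. The embryo outcome is narrower than its hypothesis and conflicts with the day-6 grade; the size of that gap cannot be judged from the protocol. The missing follicle count is a minor list mismatch. Only secondary outcomes are touched.

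**What to change.** 1. In Section 7.6, replace the ratio with MII oocytes divided by total oocytes retrieved, per patient. This has a value for everyone with at least one oocyte.
2. Reconcile the culture statement and the day-6 grade in Section 7.1. If day-6 embryos are frozen, word the outcome in Section 7.6 as all good-quality blastocysts cryopreserved on day 5 or day 6 by the Section 7.1 grades, so that it matches the hypothesis.
3. Add the number of follicles of at least 15 mm on the day of trigger to Section 7.5.

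The cost is a few words and one list entry. Both oocyte counts are already outcomes, and the follicle count comes from a scan already planned, so no visit, test or procedure is added. The changes are best made before outcome data are seen, so that the choice of measure cannot be questioned afterwards.
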